### 7. SAFETY ANALYSES

Safety data from the DB phase will be summarized for the subjects in the Safety Analysis Set. All safety data collected up to 30 days after permanent discontinuation of DB phase study drug and all available data for subjects who were still on study drug or on a study drug interruption will be summarized by treatment group, unless specified otherwise. All safety data will be included in data listings.

#### 7.1. Adverse Events and Deaths

### 7.1.1. Adverse Event Dictionary

Clinical and laboratory AEs will be coded using the current version of MedDRA. System organ class (SOC), high-level group term (HLGT), high-level term (HLT), preferred term (PT), and lowest-level term (LLT) will be provided in the AE dataset.

### 7.1.2. Adverse Event Severity

Adverse events are graded by the investigator as Grade 1 (mild), Grade 2 (moderate), Grade 3 (severe) or Grade 4 (life-threatening) according to toxicity criteria specified in the protocol. The severity grade of events for which the investigator did not record severity will be left as "missing" for data listings.

### 7.1.3. Relationship of Adverse Events to Study Drug

Related AEs are those for which the investigator selected "Related" on the AE eCRF to the question of "Related to Study Treatment." Events for which the investigator did not record relationship to study drug will be considered related to study drug for summary purposes. However, by-subject data listings will show the relationship as missing.

### 7.1.4. Serious Adverse Events

Serious adverse events (SAEs) will be identified and captured as SAEs if the AEs met the definitions of SAEs that were specified in the study protocol. SAEs captured and stored in the clinical database will be reconciled with the SAE database from the Gilead Pharmacovigilance and Epidemiology (PVE) Department before data finalization.

### 7.1.5. Treatment-Emergent Adverse Events

### 7.1.5.1. Definition of Treatment-Emergent Adverse Events

Treatment-emergent adverse events (TEAEs) are defined as 1 or both of the following:

- Any AEs with an onset date on or after the study drug start date and no later than 30 days after permanent discontinuation of the study drug (regardless of study drug interruptions), or
- Any AEs leading to premature discontinuation of study drug.

The TEAE definitions will be applied to the DB phase data and the OLE phase data, separately. When DB phase data are used, AEs onset date will be compared with the DB phase first dose date and last dose date and premature discontinuation of study drug refers to study drug discontinuation in the DB phase. An AE meeting the TEAE criteria will be considered as a TEAE in the DB phase. When OLE phase data are used, AEs onset date will be compared with the OLE phase first dose date and last dose date and premature discontinuation of study drug refers to study drug discontinuation in the OLE phase. An AE meeting the TEAE criteria will be considered as a TEAE in the OLE phase.

### 7.1.5.2. Incomplete Dates

If the onset date of the AE is incomplete and the AE stop date is not prior to the first dosing date of study drug, then the month and year (or year alone if month is not recorded) of onset determine whether an AE is treatment emergent. The event is considered treatment emergent for the DB phase if both of the following 2 criteria are met:

- The month and year (or year) of the AE onset is the same as or after the month and year (or year) of the first dosing date of study drug, and
- The month and year (or year) of the AE onset is the same as or before the month and year (or year) of the date corresponding to the minimum of

30 days after the date of the DB phase last dose of study drug, and

the OLE phase first dose date minus 1 day.

The event is considered treatment emergent for the OLE phase if both of the following 2 criteria are met:

- The month and year (or year) of the AE onset is **after** the month and year (or year) of the first dosing date of OLE phase study drug, and
- The month and year (or year) of the AE onset is **the same as or before** the month and year (or year) of the date corresponding to 30 days after the date of the last dose of OLE phase study drug.

An AE with completely missing onset and stop dates, or with the onset date missing and a stop date marked as ongoing or on or after the first dosing date of randomized study drug, will be considered to be treatment emergent for the DB phase. In addition, an AE with the onset date missing and incomplete stop date with the same or later month and year (or year alone if month is not recorded) as the first dosing date of the randomized study drug will be considered treatment emergent for the DB phase.

### 7.1.6. Summaries of Adverse Events and Deaths

The number and percentage of subjects who experienced at least 1 TEAE during the DB phase will be provided and summarized by SOC, HLT, PT, and treatment group. For other AEs described below, summaries will be provided by SOC, PT, and treatment group using the Safety Analysis Set:

- Any Grade 2, 3, or 4 treatment-emergent AEs
- Any Grade 3 or 4 treatment-emergent AEs
- All treatment-emergent study drug-related AEs
- Any Grade 2, 3, or 4 treatment-emergent study drug-related AEs
- Any Grade 3 or 4 treatment-emergent study drug-related AEs
- All treatment-emergent SAEs
- All treatment-emergent study drug-related SAEs
- All treatment-emergent AEs that caused premature discontinuation from study drug

A brief, high-level summary of AEs described above will be provided by treatment group and by the number and percentage of subjects who experienced the above AEs. Treatment-emergent deaths observed in the DB phase will be also included in this summary.

Treatment-emergent death refers to deaths that occurred between the DB phase first dose date and the DB phase last dose date plus 30 days (inclusive).

Multiple events will be counted only once per subject in each summary. Adverse events will be summarized and listed first in alphabetic order of SOC and HLT within each SOC (if applicable), and then by PT in descending order of total frequency within each SOC. For summaries by severity grade, the most severe grade will be used for those AEs that occurred more than once in an individual subject during the study.

In addition to the above summary tables, all treatment-emergent AEs, Grade 3 or 4 treatment-emergent AEs, treatment-emergent study drug-related AEs, Grade 2, 3, or 4 treatment-emergent study drug-related AEs, and treatment-emergent SAEs will be summarized by PT only, in descending order of total frequency.

In addition, data listings will be provided for the following:

- All AEs
- Grade 3 and 4 AEs

- SAEs
- Study Drug-Related SAEs
- Deaths
- AEs leading to premature discontinuation of study drug

### 7.2. Laboratory Evaluations

Laboratory data collected during the DB phase of the study will be analyzed and summarized using both quantitative and qualitative methods. Summaries of laboratory data will be provided for the Safety Analysis Set. The analysis will be based on values reported in conventional units. When values are below the LOQ, they will be listed as such, and the imputed value will be used for the purpose of calculating summary statistics as specified in Section 3.7.

A by-subject listing for laboratory test results will be provided by subject ID number and visit in chronological order for hematology, serum chemistry, and urinalysis separately for all data collected from both phases of the study. Values falling outside of the reference range and/or having a severity grade of 1 or higher on the Gilead Grading Scale for Severity of Adverse Events and Laboratory Abnormalities will be flagged in the data listings, as appropriate.

### 7.2.1. Summaries of Numeric Laboratory Results

Descriptive statistics will be provided by treatment group for each laboratory test specified in the study protocol as follows:

- Baseline values
- Values at each postbaseline analysis window
- Change from baseline at each postbaseline analysis window
- Percentage change from baseline to each postbaseline analysis window (if specified)

A baseline laboratory value will be defined as the last nonmissing value obtained on or prior to the date of first dose of study drug. Change from baseline to a postbaseline visit will be defined as the postbaseline value minus the baseline value. The mean, median, Q1, Q3, minimum, and maximum values will be displayed to the reported number of digits; SD values will be displayed to the reported number of digits plus 1.

In the case of multiple values in an analysis window, data will be selected for analysis as described in Section 3.8.3.

### **Calcium Corrected for Albumin**

Calcium corrected for albumin will be calculated and summarized for the study. The following formula will be used when both serum calcium and albumin results for a given blood drawn are available and serum albumin value is < 4.0 g/dL.

• Calcium corrected for albumin (mg/dL) serum calcium (mg/dL) +  $0.8 \times (4.0 \text{ albumin (g/dL)})$ 

Toxicity grading for calcium will be applied based on the corrected values.

### **Estimated GFR**

The Cockcroft Gault formula will be used to calculate eGFRCG:

• eGFRCG (mL/min) [(140 age (yrs)) × weight (kg) × (0.85 if female)] / (SCr (mg/dL) × 72), where weight is total body mass in kilograms, and SCr is serum creatinine.

### 7.2.2. Graded Laboratory Values

The Gilead Grading Scale for Severity of Adverse Events and Laboratory Abnormalities will be used for assigning toxicity grades (0 to 4) to laboratory results for analysis. Grade 0 includes all values that do not meet the criteria for an abnormality of at least Grade 1. For laboratory tests with criteria for both increased and decreased levels, analyses for each direction (ie, increased, decreased) will be presented separately.

If there is any laboratory toxicity grading scale overlapping with the normal reference ranges (ie, Grade 1 scale overlaps with normal reference ranges), laboratory values that are within the normal range will be Grade 0, except for lipid tests.

For triglycerides, LDL, and cholesterol, the protocol-specified toxicity grading scale is for fasting test values, so nonfasting lipid results (or lipid results without a known fasting status) will not be graded or summarized by toxicity grades.

### 7.2.2.1. Treatment-Emergent Laboratory Abnormalities

Only the laboratory abnormalities during the randomize phase will be summarized. Treatment-emergent laboratory abnormalities are defined as values that increase at least 1 toxicity grade from baseline at any postbaseline time point, up to 30 days after permanent discontinuation of randomized study drug or the last available date for subjects who were still on study drug or on a study drug interruption during the DB phase at the time of analysis. If the relevant baseline laboratory value is missing, any abnormality of at least Grade 1 observed within the time frame specified above will be considered treatment-emergent.

Fasting glucose and nonfasting glucose (including glucose results without a known fasting status) are graded based on different grading scales as specified in the protocol. Fasting status was recommended for postbaseline lipids and not required for Screening lipid assessments. For nonfasting glucose (including glucose results without a known fasting status), fasting glucose, fasting total cholesterol, fasting triglycerides and fasting LDL, maximum postbaseline grade, instead of treatment-emergent grade, will be summarized, as fasting status at baseline was approximately half fasting and half nonfasting; therefore, whether an abnormality is treatment-emergent or not cannot be determined for approximately half of the subjects.

### 7.2.2.2. Summaries of Laboratory Abnormalities

The following summaries (number and percentage of subjects) for treatment-emergent laboratory abnormalities will be provided by lab test and treatment group; subjects will be categorized according to the most severe postbaseline abnormality grade for a given lab test:

- Treatment-emergent laboratory abnormalities
- Treatment-emergent Grade 3 and 4 laboratory abnormalities
- Treatment-emergent Grade 2, 3 and 4 laboratory abnormalities

For all summaries of laboratory abnormalities, the denominator is the number of subjects with any nonmissing postbaseline values up to 30 days after permanent discontinuation of study drug.

A by-subject listing of all laboratory abnormalities and Grade 3 or 4 laboratory abnormalities will be provided by subject ID number and visit in chronological order.

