- a All study visits in the double-blind phase are to be scheduled relative to the Day 1 visit date. Visit windows are ± 2 days of the protocol-specified date through Week 12, ± 14 days of the protocol-specified date through the end of blinded treatment phase visit, unless otherwise specified.
- b end of blinded treatment phase visit to occur after all participants reach Week 96.
- c Study visits are to be completed within ± 14 days of the protocol-specified visit date based on the end of blinded treatment phase visit.
- d Participants will continue study visits every 12 weeks in the OL phase up to OL Week 96 (not including OL Week 96). From OL Week 96, refer to [Appendix 3](#).

- e For 30-Day Follow-up visits conducted prior to OL Week 96, must be completed 30 days after discontinuing study drug. All participants who have received at least one dose of study drug will be required to complete a follow-up visit. For the purpose of scheduling a 30-Day Follow-Up visit, a ± 14 days window may be used.
- f For Early Study Drug Discontinuation Visits conducted prior to OL Week 96, visit to occur within 72 hours of last dose of study drug. Participants will be asked to continue attending the scheduled study visits through the end of blinded treatment phase visit.
- g Vital signs measurement including blood pressure, pulse, respiration rate, and temperature. After the Day 1 visit, vital signs completed when clinically indicated.
- h Chemistry profile: alkaline phosphatase, AST, ALT, GGT, total bilirubin, direct and indirect bilirubin, total protein, albumin, LDH, bicarbonate, BUN, calcium, chloride, creatinine, glucose, phosphorus, magnesium, potassium, sodium, uric acid, and amylase (reflex lipase testing is performed in participants with total amylase $> 1.5 \times$ ULN).
- i Complete blood count (CBC) with differential and platelet count
- j [REDACTED]
- k Local STI testing for syphilis.
- l [REDACTED]
- m For possible PK, virology, and/or safety testing
- n Computer-assisted self-interview (CASI)
- o If Day 1 is completed > 7 days after the screening visit

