- c Study visits are to be completed within ± 14 days of the protocol specified visit date based on the End of Blinded Treatment Phase visit.
- d Subjects will continue study visits every 12 weeks until study drug F/TAF is commercially available in their region (except Denmark and the United Kingdom).
- e Must be completed 30 days after discontinuing study drug. All subjects who have received at least one dose of study drug will be required to complete a follow-up visit. For the purpose of scheduling a 30 Day Follow Up visit, a ± 14 days window may be used.
- f Early Study Drug Discontinuation visit to occur within 72 hours of last dose of study drug. Subjects will be asked to continue attending the scheduled study visits through the End of Blinded Treatment Phase visit.
- g Vital signs measurement including blood pressure, pulse, respiration rate, and temperature. After the Day 1 visit, vital signs completed when clinically indicated.
- h Chemistry profile: alkaline phosphatase, AST, ALT, GGT, total bilirubin, direct and indirect bilirubin, total protein, albumin, LDH, bicarbonate, BUN, calcium, chloride, creatinine, glucose, phosphorus, magnesium, potassium, sodium, uric acid, and amylase (reflex lipase testing is performed in subjects with total amylase > 1.5 × ULN).

- i Complete blood count (CBC) with differential and platelet count.
- j Blood sample collected for DBS testing to be stored at central laboratory.
- k Local STI testing for syphilis.
- 1 Trough PK blood samples to evaluate the pharmacokinetics of intracellular TFV DP and FTC TP, plasma TFV and FTC. The blood sample should be taken approximately 24 hours after the last dose of study drug and prior to administration of study drug the day of the visit.
- n Computer assisted self interview (CASI).
- o If Day 1 is completed > 7 days after the screening visit.
- p 4th generation rapid HIV 1 Ab/Ag or 3rd generation rapid HIV 1 Ab test may be used. If 4th generation rapid HIV 1 Ag/Ab or 3rd generation rapid HIV 1 Ab test is positive, a retest will be completed. At Screening or Day 1, if rapid retest is positive the subject is a screen failure. At all other visits if rapid retest is positive, then HIV 1 RNA by PCR test and sample collection for possible genotypic testing will be completed.

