# 26) Graded Laboratory Abnormalities Summary

The following labels will be used for treatment-emergent laboratory abnormalities and treatment-emergent Grade 3 or 4 laboratory abnormalities summary tables and listings:

Battery	Lab Test Label Used in l-labtox Listing	Toxicity Direction	Lab Test Label Used in t-labtox Table
	Hemoglobin	Decrease	Hemoglobin (Decreased)
	Lymphocytes	Decrease	Lymphocytes (Decreased)
Hematology	Neutrophils	Decrease	Neutrophils (Decreased)
	Platelets	Decrease	Platelets (Decreased)
	WBC	Decrease	WBC (Decreased)
	Albumin	Decrease	Albumin (Decreased)
	Alkaline Phosphatase	Increase	Alkaline Phosphatase (Increased)
	ALT	Increase	ALT (Increased)
	Amylase	Increase	Amylase (Increased)
	AST	Increase	AST (Increased)
	Bicarbonate	Decrease	Bicarbonate (Decreased)
	Corrected Calcium	Increase	Corrected Calcium (Hypercalcemia)
	Corrected Calcium	Decrease	Corrected Calcium (Hypocalcemia)
	Creatinine	Increase	Creatinine (Increased)
	GGT	Increase	GGT (Increased)
	Lipase	Increase	Lipase (Increased)
	Magnesium	Decrease	Magnesium (Hypomagnesemia)
	Phosphate	Decrease	Phosphate (Hypophosphatemia)
Chemistry	Serum Glucose (Fasting)	Increase	Serum Glucose (Fasting, Hyperglycemia)
Chemistry	Serum Glucose (Fasting)	Decrease	Serum Glucose (Fasting, Hypoglycemia)
	Serum Glucose (Nonfasting)	Increase	Serum Glucose (Nonfasting, Hyperglycemia)
	Serum Glucose (Nonfasting)	Decrease	Serum Glucose (Nonfasting, Hypoglycemia)
	Serum Potassium	Increase	Serum Potassium (Hyperkalemia)
	Serum Potassium	Decrease	Serum Potassium (Hypokalemia)
	Serum Sodium	Increase	Serum Sodium (Hypernatremia)
	Serum Sodium	Decrease	Serum Sodium (Hyponatremia)
	Total Bilirubin	Increase	Total Bilirubin (Hyperbilirubinemia)
	Total Cholesterol (Fasting)	Increase	Total Cholesterol (Fasting, Hypercholesterolemia)
	Triglycerides (Fasting)	Increase	Triglycerides (Fasting, Increased)
	LDL (Fasting)	Increase	LDL (Fasting, Increased)
	Urea Nitrogen (BUN)	Increase	Urea Nitrogen (Increased)
	Uric Acid	Increase	Uric Acid (Hyperuricemia)
	Uric Acid	Decrease	Uric Acid (Hypouricemia)

Battery	Lab Test Label Used in l-labtox Listing	Toxicity Direction	Lab Test Label Used in t-labtox Table	
	Urine Blood (Dipstick)	Increase	Urine RBC (Hematuria, Quantitative or Dipstick)*	
T.I	Urine Glucose	Increase	Urine Glucose (Glycosuria)	
Urinalysis	Urine Protein	Increase	Urine Protein (Proteinuria)	
	Urine RBC (Quantitative)	Increase	Urine RBC (Hematuria, Quantitative or Dipstick)*	

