\* Due to the reflexive nature of the quantitative urine RBC test, results will be combined with the dipstick test of urine blood as described below. General rule is that urine RBC (Quantitative) should always be used first (if available), no matter it is collected at the same time of Urine Blood (Dipstick) or not. The combined Urine RBC (hematuria, Quantitative or Dipstick) toxicity grade will be used for "Maximum treatment emergent toxicity grade" summary.

Is Post-BL Urine RBC (Quant.) Result Available?	Is BL Urine RBC (Quant.) Result Available?	Is Post-BL Urine Blood (Dipstick) Result Available?	Is BL Urine Blood (Dipstick) Result Available?	How to Determine Treatment- Emergent Toxicity for "Urine RBC (Hematuria, Quantitative or Dipstick)"
Yes	Yes	-	-	Compare post-BL Urine RBC (Quant.) toxicity grade to BL Urine RBC (Quant.) toxicity grade. If post- BL toxicity is greater than BL toxicity, then treatment-emergent
Yes	No	-	-	Treatment-emergent. Use post-BL Urine RBC (Quant.) toxicity grade.
No	-	Yes	Yes	Compare post-BL Urine Blood (Dipstick) toxicity grade to BL Urine Blood (Dipstick) toxicity grade. If post-BL toxicity is greater than BL toxicity, then treatment-emergent
No	-	Yes	No	Treatment-emergent. Use post-BL Urine Blood (Dipstick) toxicity grade.
No	-	No	-	Do not count subject in the denominator for "Urine RBC (Hematuria, Quantitative or Dipstick)"

BL Baseline. Quant Quantitative. "" means any value can be present (or it can be missing), as it does not affect the classification

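### Lipase is tested only when amylase exceeds 1.5 × ULN, so a lipase abnormality rate among those tested is conditional on raised amylase and not comparable with the other laboratory rows

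*SAP*

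**What the plan says.** **When lipase is measured.** The chemistry profile in Protocol 6.2.1 (screening), 6.3 (blinded visits) and Appendix 2 footnote h includes amylase but not lipase. Lipase follows only on a trigger: "reflex lipase testing is performed in subjects with total amylase > 1.5 × ULN" (SAP Appendix 1, footnote h, repeating the protocol). Chemistry is drawn at screening and not on Day 1, so baseline lipase depends on the same trigger.

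**How it is graded.** In Protocol Appendix 5, Grade 2 total amylase starts just above 1.5 × ULN. Lipase has its own bands, with Grade 1 starting just above 1.0 × ULN.

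**How it is reported.** SAP Appendix 12 item 26 lists increased lipase among the row labels, introduced by: "The following labels will be used for treatment-emergent laboratory abnormalities and treatment-emergent Grade 3 or 4 laboratory abnormalities summary tables and listings". SAP 7.2.2.2 makes these summaries by laboratory test and states that "subjects will be categorized according to the most severe postbaseline abnormality grade for a given lab test". The denominator rule for all of them is "For all summaries of laboratory abnormalities, the denominator is the number of subjects with any nonmissing postbaseline values", with the window closing 30 days after study drug is stopped for good.

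**Missing baseline.** On what counts as treatment-emergent, SAP 7.2.2.1 says "If the relevant baseline laboratory value is missing, any abnormality of at least Grade 1 observed within the time frame specified above will be considered" so. Protocol 8.5.3 has the same rule.

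**The other reflex test.** For quantitative urine RBC, item 26 recognises that the test is reflexive and combines it with the dipstick. Someone with neither postbaseline result is handled thus: "Do not count subject in the denominator for" that row. There is no corresponding rule or footnote for lipase.

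**The concern.** Most rows in the abnormality tables, such as ALT or creatinine, come from tests done at every scheduled blinded-phase visit. Their denominators will be close to the whole Safety Analysis Set. The lipase denominator, on the test-by-test reading, contains only people whose amylase was already at Grade 2 or above. The two kinds of percentage would sit in one table under one heading, and nothing would tell the reader that they answer different questions.

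The incidence of treatment-emergent laboratory toxicities is among the other secondary endpoints (Protocol 3.1.2 and 8.1.3), so a reader would take the lipase figure as an incidence on drug. The two arms' percentages would also not be a comparison of randomised groups, because entry to the denominator depends on a postbaseline amylase result that treatment could influence.

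**Working it through.** The documents give no lipase rate, amylase rate or number reflex-tested, so there is no planned figure to reproduce. The check is a set of proportions.

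**Inputs from the documents**
- Reflex trigger: amylase > 1.5 × ULN (Protocol Appendix 2; SAP Appendix 1).
- Safety Analysis Set: 5387 (SAP Appendix 3). Assuming equal arms, 5387 / 2 ≈ 2694 per arm.

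**Assumptions, not in the documents**
- f, share of participants reflex-tested postbaseline: 1% to 10%.
- p, share of those tested with lipase above ULN: 20% to 60%; 40% is used below.
- u, share of untested participants with unmeasured lipase elevation: 0% to 20%.

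**Formulas**
- Printed percentage, test-specific denominator: p.
- Observed cases over all participants: f × p.
- Rate if everyone had been tested: f × p + (1 − f) × u.

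**Step 1. Against observed cases over all participants.** The ratio is p / (f × p) = 1/f, whatever p is. With p = 40%:

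| f | Tested per arm | Printed | Observed cases / all | Ratio |
|---|---|---|---|---|
| 1% | 27 | 40% | 0.40% | 100 |
| 2% | 54 | 40% | 0.80% | 50 |
| 5% | 135 | 40% | 2.0% | 20 |
| 10% | 269 | 40% | 4.0% | 10 |

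**Step 2. Against the rate if everyone had been tested.** With f = 5% and p = 40%:

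| u | All-participant rate | Printed / all-participant |
|---|---|---|
| 0% | 0.02 + 0.95 × 0 = 2.0% | 20 |
| 2% | 0.02 + 0.95 × 0.02 = 3.9% | 10.3 |
| 5% | 0.02 + 0.95 × 0.05 = 6.75% | 5.9 |
| 10% | 0.02 + 0.95 × 0.10 = 11.5% | 3.5 |
| 20% | 0.02 + 0.95 × 0.20 = 21.0% | 1.9 |

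**Step 3. Direction.** The printed figure exceeds the all-participant rate when p > f × p + (1 − f) × u. This reduces to p > u. The overstatement therefore needs only that elevation be more common in tested than in untested participants. At p = u it vanishes.

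**Step 4. The missing-baseline rule.** A participant with no baseline lipase and a Grade 1 or higher postbaseline value is treatment-emergent under SAP 7.2.2.1. If baseline were instead set to Grade 0, the same value would be a rise of at least one grade and still be treatment-emergent. The numerator is the same either way, so the denominator is what needs correcting.

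**The case against.** **The denominator wording is not explicit.** SAP 7.2.2.2 does not say that the nonmissing values must be for that test, whereas SAP 7.2.4 on liver tests does tie its denominator to the tests being evaluated. If any laboratory value qualifies, nothing is inflated. This stands in part: the test-specific reading is an inference. It is a strong one, because the summaries are made by test and the urine RBC rule drops untested people from that row. On the other reading the row is a floor, because most of those counted were probably never tested for lipase, and it is not labelled as one. The text needs attention either way.

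**The size is assumed.** This stands. A reader might infer that the lipase rate will be wrong by tens of times. The documents do not support that, because f, p and u are all unknown and the 1/f ratio treats every untested person as normal.

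**The missing-baseline rule.** A reader might infer that it is a second fault. As step 4 shows, assigning Grade 0 would change no classification. The rule is also in the protocol, and the SAP keeps it in its urine RBC solution.

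**The urine RBC parallel is loose.** This stands as far as merging goes. The two hematuria measures share one row, while amylase and lipase are different enzymes with separate rows, so combining them is not an option. The parallel shows only that the SAP recognised a reflex test elsewhere.

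**The consequence is small.** This largely stands. SAP 7.2.2.2 plans counts and percentages with no test, the case count does not depend on the denominator, by-subject listings are provided, and raised amylase appears in its own row on the broad denominator.

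**Conclusion.** The point holds, on the test-specific reading of SAP 7.2.2.2. The planned lipase percentage would be conditional on Grade 2 or higher amylase, in a subset formed after randomisation, and would not be an incidence comparable with neighbouring rows. It overstates the all-participant rate if p > u, which is the expected direction for a test triggered by raised amylase.

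The size is not computable from the documents. Relative to observed cases over all participants it is 1/f, or 10- to 100-fold for an assumed f of 10% to 1%. Relative to the true rate it may be much less, for example 1.9-fold at f = 5%, p = 40% and u = 20%.

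A reader might also infer that the trial's safety comparison as a whole is compromised. It is not. The effect is limited to lipase in the descriptive abnormality tables, both arms follow the same rule, and no alpha-controlled endpoint or power figure is touched.

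**What to change.** In SAP 7.2.2.2 and Appendix 12 item 26:

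1. Define the lipase denominator as all Safety Analysis Set participants with a postbaseline amylase value in the same time window.
2. Show the number reflex-tested per arm beside the row.
3. Footnote the row: lipase tested only when amylase > 1.5 × ULN; percentage is a lower bound.

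No change to baseline handling is needed.

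The cost is a sentence in the SAP, a footnote and a programming change for one row. The downside is that the percentage becomes a floor, because lipase elevation without the amylase trigger goes unseen. The footnote and the tested counts make that visible.
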